16.45 Data & Safety Monitoring

- 16.451 The principal investigator(s) and the study statistician will review the study at least every quarter to identify accrual, adverse event, and any endpoint problems that might be developing. The Mayo Clinic Cancer Center (MCCC) Data Safety Monitoring Board (DSMB) is responsible for reviewing accrual and safety data for this trial at least twice a year, based on reports provided by the MCCC Statistical Office.
- 16.452 **Adverse Event Stopping Rule:** The stopping rules specified below are based on the knowledge available at study development. We note that the rule may be adjusted in the event of either (1) the study re-opening to accrual or (2) at any time during the conduct of the trial and in consideration of newly acquired information regarding the adverse event profile of the treatments under investigation. The study team may choose to suspend accrual because of unexpected adverse event profiles that have not crossed the specified rule below.

Accrual will be temporarily suspended if at any time we observe events considered at least possibly related to study treatment (i.e. an adverse event with attribute specified as "possible," "probable," or "definite") that satisfy any of the following:

Phase I (Includes all dose levels in phase I): By the nature of the "cohorts of three" phase I study design, toxicity (i.e., adverse events that are possibly, probably or definitely related to study treatment) stopping

rules are in place for each dose level. Specifically, if 2 or more dose-limiting toxicities (DLTs) are observed during cycle 1 at any given dose level, accrual to that dose level will be stopped, and patients will be accrued to the next lower dose level until a maximum of 6 patients are treated at the lower level. Note that a DLT that affects dose escalation is only that which is observed in the first cycle of treatment. However, all cycles will be reviewed and the study team will determine whether the dose level needs to be adjusted for future patients if ≥ 1 in the first 3 patients OR ≥ 2 in the first 6 patients experience a grade 4 or higher non-hematologic adverse event at least possibly related to treatment over all cycles at any given dose level

Phase II (includes all phase II patients, including Phase I patients treated at the MTD):

- if 5 or more patients in the first 15 treated patients experience a grade 4 or higher non-hematologic adverse event at least possibly related to treatment, excluding febrile neutropenia and dehydration.
- if after the first 15 patients have been treated, 30% of all patients experience a grade 4 or higher non-hematologic adverse event at least possibly related to treatment, excluding febrile neutropenia and dehydration.

We note that we will review grade 4 and 5 adverse events deemed “unrelated” or “unlikely to be related”, to verify their attribution and to monitor the emergence of a previously unrecognized treatment-related adverse event.

16.5 Results Reporting on ClinicalTrials.gov: At study activation, this study will have been registered within the “ClinicalTrials.gov” website. The Primary and Secondary Endpoints along with other required information for this study will be reported on ClinicalTrials.gov. For purposes of timing of the Results Reporting, the initial estimated completion date for the Primary Endpoint of this study is 2 years after the study opens to accrual. The definition of “Primary Endpoint Completion Date” (PECD) for this study is at the time the last patient registered has completed the response evaluation after two cycles of treatment.

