7.62 Definitions of DLT

7.621 For this protocol, DLT will be defined as an adverse event attributed (definitely, probably, or possibly related) to the study treatment and meeting the following criteria with the first cycle:

- Any grade ≥ 3 non-hematologic adverse event. The following are some of the exceptions noted:
 - Alopecia, anorexia, or fatigue.
 - Grade 3 nausea and/or vomiting if not requiring tube feeding or total parenteral nutrition TPN, or diarrhea if not requiring or prolonging hospitalization that can be managed to Grade ≤ 2 with antiemetic or antidiarrheal medications

- Grade 3 fever with neutropenia, with or without infection.
 - Grade 3 infection.
 - Grade 3 tumor lysis syndrome that resolves within 72 hours after initiation of treatment.
 - Any grade electrolyte alteration that resolves to grade ≤ 1 within 72 hours after it occurs.
- Hematological adverse events include the following:
 - Failure of platelet recovery to 50,000/mm³ by day 29
 - Failure of absolute neutrophil recovery to 1000/mm³ by Day 29

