15.5 Etoposide (VePesid®, Toposar®, VP16)

Refer to the package insert for complete prescribing information.

- 15.51 **Background:** Etoposide has been shown to delay transit of cells through the S phase and arrest cells in late S or early G2 phase. The drug may inhibit mitochondrial transport at the NADH dehydrogenase level or inhibit uptake of nucleosides into HeLa cells. It is a topoisomerase II inhibitor and appears to cause DNA strand breaks. Etoposide does not inhibit microtubular assembly.
- 15.52 **Formulation:** Commercially available for injection as:
Injection, solution: 20 mg/mL (5 mL, 25 mL, 50 mL)
- 15.53 **Preparation, storage, and stability:** Refer to package insert for complete preparation and dispensing instructions. Store intact vials at room temperature of 25°C (77°F); do not freeze. Protect from light. Etoposide should be diluted to a concentration of 0.2-0.4 mg/mL in D5W or NS for administration. Diluted solutions have concentration-dependent stability; more concentrated solutions have shorter stability times. Precipitation may occur with concentrations > 0.4 mg/mL. Following dilution 0.9% Sodium Chloride or D5W to concentrations of 0.2-0.4 mg/mL, then drug is chemically stable for 96 and 24 hours at room temperature respectively.
- 15.54 **Administration:** Refer to the treatment section for specific administration instructions. Administer standard doses over at least 30-60 minutes to minimize the risk of hypotension.
- 15.55 **Pharmacokinetic information:**
Distribution: V_d : 7-171 L/m²; poor penetration across the blood-brain barrier; CSF concentrations <5% of plasma concentrations
Protein binding: 94% to 98%
Metabolism: Hepatic via CYP3A4 and 3A5, to various metabolites.
Half-life elimination: Terminal 4-11 hours
Excretion: Urine (56%; 45% as unchanged drug) within 120 hours; feces (44%) within 120 hours
- 15.56 **Potential Drug Interactions:**
Metabolism/Transport Effects: Substrate of CYP1A2 (minor),

CYP2E1 (minor), CYP3A4 (major), P-glycoprotein; **Inhibits** CYP2C9 (weak), 3A4 (weak)

Ethanol/Herb/Nutraceutical Interactions: Avoid ethanol (may increase GI irritation). Avoid concurrent St John's wort; may decrease etoposide levels.

- 15.57 **Known potential adverse events:** Consult the package insert for the most current and complete information. **U.S. boxed warning: Severe dose-limiting and dose-related myelosuppression with resulting infection or bleeding may occur.**

Common known potential toxicities, > 10%:

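### The mandatory phase II accrual-suspension rule does not count a treatment-related death coded as febrile neutropenia, dehydration or a hematologic term, and it has no separate boundary for deaths

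*Combined protocol and SAP*

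**What the plan says.** Section 16.452 makes the pause compulsory once a criterion is met: "Accrual will be temporarily suspended if at any time we observe events considered at least possibly related to study treatment" that satisfy one of the listed conditions. Phase II has two. The first applies "if 5 or more patients in the first 15 treated patients experience a grade 4 or higher non-hematologic adverse event"; the second applies "if after the first 15 patients have been treated, 30% of all patients experience a grade 4 or higher non-hematologic adverse event". Both carry the same qualifier, so that the counted event is a "grade 4 or higher non-hematologic adverse event at least possibly related to treatment, excluding febrile neutropenia and dehydration". No criterion refers to deaths as such, and the qualifier gives no grade above which the two excluded terms count again.

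Other provisions bear on the same risk:

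- **Discretion (16.452).** "The study team may choose to suspend accrual because of unexpected adverse event profiles that have not crossed the specified rule below". The rule itself may also be adjusted during the trial.
- **Periodic review (16.451).** The principal investigators and statistician review the study at least quarterly, and the DSMB at least twice a year.
- **Death reporting (10.331).** Deaths within 30 days of the last dose, and later deaths judged related, are reported within 24 hours.
- **Attribution check (16.452).** Grade 4 and 5 events called unrelated or unlikely to be related are re-examined.
- **Termination and rapid accrual (16.33, 16.314).** Toxicity is weighed in any decision to terminate, and accrual may be suspended if it is especially rapid.

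**The concern.** Whether a neutropenic death reaches the mandatory rule depends on the CTCAE term chosen for it. Coded as sepsis or pneumonia, it is a grade 5 non-hematologic event and counts. Coded as febrile neutropenia, which section 10.52 has graded at every evaluation, it does not. Two sites could report clinically similar deaths and move the rule differently.

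The phase I text is narrower. Among the DLT exceptions in 7.621, the entry for this toxicity is "Grade 3 fever with neutropenia, with or without infection", which does not mention grades 4 or 5. The plan does not say why the phase II exclusion is wider.

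The toxicity is a foreseeable one for this regimen. Section 15.17 lists febrile neutropenia among the common lenalidomide events, and the etoposide boxed warning in 15.57 reads "Severe dose-limiting and dose-related myelosuppression with resulting infection or bleeding may occur".

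A death that does count weighs no more than a reversible grade 4 event. At stake is whether a run of related deaths would oblige anyone to pause enrollment, or would rest on judgment and the review calendar.

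**Working it through.** The plan gives no operating characteristics for this rule, so there is no stated figure to reproduce.

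**Inputs**
- Boundaries: 5 of the first 15, then 30% of all patients (16.452).
- Phase II size: 45 evaluable patients (16.12).
- Accrual: 4 to 5 evaluable patients per month (16.13).
- Fatal event rates: none are given. The rates below are assumptions, shown as a range.

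**1. What counts, by coding of a related death**

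| Coded term | Counts toward the rule? |
|---|---|
| Sepsis, pneumonia or other non-hematologic term | Yes, as one patient |
| Febrile neutropenia | No, excluded at any grade |
| Dehydration | No, excluded at any grade |
| Hematologic term | No, outside the rule |

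For the last three rows the contribution is 0, whatever the number of deaths.

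**2. How many counted deaths need no pause**

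Assume no other counted events.
- First 15 patients: the boundary is 5, so 4 deaths (4/15 = 26.7%) do not cross.
- After 15: the boundary is the smallest whole number at or above 0.30 × n. It is 5 at n = 16, 6 at n = 17 and n = 20, 9 at n = 30, and 14 at n = 45 (0.30 × 45 = 13.5).
- At 45 patients: 13/45 = 28.9% does not cross; 14/45 = 31.1% does.

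**3. What simply counting the excluded deaths would achieve**

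Suppose febrile neutropenia deaths are the only events and they are counted in the existing rule. For the first 15 patients, P(X ≥ 5) = 1 − Σ C(15, x) pˣ (1 − p)¹⁵⁻ˣ, summed over x = 0 to 4. The probability by 45 patients comes from an exact patient-by-patient recursion over the boundaries in step 2, checking the rule after every patient.

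| Assumed rate p | Expected deaths in 45 (45 × p) | Pause as written | Pause by 15 if counted | Pause by 45 if counted |
|---|---|---|---|---|
| 5% | 2.25 | 0 | 0.001 | 0.001 |
| 10% | 4.5 | 0 | 0.013 | 0.022 |
| 15% | 6.75 | 0 | 0.062 | 0.110 |
| 20% | 9 | 0 | 0.164 | 0.297 |

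Counting these deaths removes the dependence on coding but rarely triggers a pause by itself. In practice non-fatal grade 4 events also count, so the real probabilities would be higher.

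**4. How soon a review of each related death would act**

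P(at least one) = 1 − (1 − p)ⁿ. By 15 patients this is 0.537 at 5% and 0.794 at 10%.

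**5. Enrollment between scheduled reviews**
- Quarterly: 3 months × 4 to 5 = 12 to 15 patients.
- Half-yearly: 6 months × 4 to 5 = 24 to 30 patients, over half of 45.

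**The case against.** The strongest reply is that the rule does count most related deaths. Grade 4 or higher includes grade 5, and fatal sepsis, pneumonia or hemorrhage would all count. The etoposide warning itself concerns infection and bleeding, which would often be coded to such terms. This stands, and it limits the point to deaths coded to febrile neutropenia, dehydration or a hematologic term.

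A reader might infer that the rule is blind to the toxicity most likely to kill. The documents give no rate to support that. Section 1.11 describes R-ICE as very well tolerated, and section 1.2 reports that adding lenalidomide to it caused no serious adverse events in an earlier trial.

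A reader might also infer that the discretionary clause cannot apply because febrile neutropenia is an expected event. Section 10.2 treats an event as unexpected when its observed severity is not the listed one, and 15.17 lists febrile neutropenia without a fatal grade. The clause could therefore be used; it remains optional.

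The contrast with phase I is suggestive only. Section 7.621 calls its list some of the exceptions, so it is not exhaustive, and it defines cycle 1 DLTs for dose finding. The phase I all-cycles review is also confined to non-hematologic events, and 10.52 classes febrile neutropenia under blood and lymphatic disorders, so whether it counts there is unclear. Failure of blood counts to recover is handled for the individual patient in Table 8.2.

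The lower creatinine clearance limit in phase II (30 against 60 ml/min, section 3.17) does not by itself show that toxicity will exceed phase I, because the same section points to a lenalidomide dose adjustment for those patients.

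Finally, quarterly review and 24-hour reporting mean that deaths would be known. That is true, but neither carries a boundary or an obligation to pause.

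**Conclusion.** The point holds for the mandatory rule. Related deaths coded to febrile neutropenia, dehydration or a hematologic term add nothing to it. Related deaths of counted types can reach 4 of 15, or 13 of 45, without a required pause if no other counted events occur. These statements follow from the text and need no assumed rate. The second trigger is read as at least 30% of all patients treated so far.

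Two stronger conclusions do not follow. The documents do not show that fatal myelosuppression would go unnoticed, since deaths are reported within 24 hours and the team may suspend accrual by choice. Nor do they show that fatal febrile neutropenia is likely. The probabilities in the working rest on assumed rates of 5% to 20%, with no other counted events and a check after every patient.

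This is a cheap improvement to a stated safety rule. It does not affect the efficacy design.

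**What to change.** In 16.452, phase II:

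1. Limit the febrile neutropenia and dehydration exclusion to events below grade 5. State that every grade 5 event judged possibly, probably or definitely related counts, whatever its CTCAE term or organ class.
2. Because step 1 alone seldom triggers the rule, require that each related death reported under 10.331 receives a prompt, documented review by the study team and the DSMB on whether to suspend accrual, without waiting for the quarterly or half-yearly review.

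An automatic pause after every single related death is more debatable. A prompt review gives a timely decision without imposing that.

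The cost is two sentences. No new data are needed, because the deaths already arrive within 24 hours. The downside is slightly more frequent reviews and possible short accrual pauses. At assumed related-death rates of 5% and 10%, 45 patients would generate on average 45 × 0.05 = 2.25 and 45 × 0.10 = 4.5 reviews.

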16.6 Inclusion of Women and Minorities

16.61 This study will be available to all eligible patients, regardless of race, gender, or ethnic origin.

16.62 There is no information currently available regarding differential effects of this regimen in subsets defined by race or gender, and there is no reason to expect such differences to exist. Therefore, although the planned analysis will, as always, look for differences in treatment effect based on racial and gender groupings, the sample size is not increased in order to provide additional power for subset analyses.

- 16.63 The geographical region served by ACCRU, has a population which includes approximately 5-7% minorities. Based on prior ACCRU studies involving similar disease sites, we expect about 5-7% of patients will be classified as minorities by race and about 40% of patients will be women. Expected sizes of racial by gender subsets are shown in the following table:

Accrual Targets			
Ethnic Category	Sex/Gender		
	Females	Males	Total
Hispanic or Latino	0	1	1
Not Hispanic or Latino	25	37	62
Ethnic Category: Total of all subjects	25	38	63
Racial Category			
American Indian or Alaskan Native	0	0	0
Asian	0	1	1
Black or African American	1	1	2
Native Hawaiian or other Pacific Islander	0	0	0
White	24	36	60
Racial Category: Total of all subjects	25	38	63

Ethnic Categories: **Hispanic or Latino** – a person of Cuban, Mexican, Puerto Rican, South or Central American, or other Spanish culture or origin, regardless of race. The term “Spanish origin” can also be used in addition to “Hispanic or Latino.”

Not Hispanic or Latino

Racial Categories: **American Indian or Alaskan Native** – a person having origins in any of the original peoples of North, Central, or South America, and who maintains tribal affiliations or community attachment.
Asian – a person having origins in any of the original peoples of the Far East, Southeast Asia, or the Indian subcontinent including, for example, Cambodia, China, India, Japan, Korea, Malaysia, Pakistan, the Philippine Islands, Thailand, and Vietnam. (Note: Individuals from the Philippine Islands have been recorded as Pacific Islanders in previous data collection strategies.)
Black or African American – a person having origins in any of the black racial groups of Africa. Terms such as “Haitian” or “Negro” can be used in addition to “Black or African American.”
Native Hawaiian or other Pacific Islander – a person having origins in any of the original peoples of Hawaii, Guam, Samoa, or other Pacific Islands.
White – a person having origins in any of the original peoples of Europe, the Middle East, or North Africa.

17.0 Pathology Considerations/Tissue Biospecimens

17.1 Tissue Biospecimen Submission

17.11 Summary Table of Tissue Biospecimens for This Protocol

Type of tissue biospecimen to submit	Mandatory or optional	When to submit	Reason for submission (background/methodology section)	Where to find specific details for biospecimen submission
All H&E diagnostic slides	Mandatory	Within 30 days after registration	Pathology Central review	See Section 17.2
CD20 stained slide	Mandatory		Pathology Central review	See Section 17.2
Formalin-fixed paraffin-embedded (FFPE) tissue block or (15) 4µm unstained slides with (1) corresponding H&E stained slide	Mandatory	Within 30 days after registration	Correlative Studies (Section 17.5)	Section See section 17.3

If an institution is not able to provide the optional FFPE tissue, it does not cause the patient to be ineligible; however, the collection of these tissues is **strongly recommended**.

17.2 All Diagnostic Slides for Confirmation of Diagnosis (**Mandatory**)

17.21 The following materials below are mandatory (unless indicated otherwise) and required for shipment:

- Diagnostic H&E Stained Slides from Most Recent Tumor Tissue Biopsy
- CD20 stained slide
- Lymphoma Pathology Reporting Form
- Surgical Pathology Report
- Tumor Tissue Immunohistochemistry or Immunophenotyping by Flow Cytometry Report (if available)
- Pre-study Bone Marrow Biopsy Report (if available)
- Pre-study Peripheral Blood Immunophenotyping by Flow Cytometry Report (if available)

Note: Include the ACCRU patient ID number on all materials listed above.

17.22 The diagnostic slide(s) must be appropriately packed to prevent damage (e.g., slides should be placed in appropriate slide container) and placed in an individual plastic bag. Label the bag with the protocol number, ACCRU patient ID number, and patient initials.

17.23 Verify that Section 1 of the Lymphoma Pathology Reporting Form is completed and filled in correctly.

17.24 Review is being performed at the ACCRU Research Base at Mayo Clinic Rochester. Ship all diagnostic slides and accompanying materials as follows:

17.251 Mayo Clinic Rochester (MCR) patients only: please forward pathology material to [REDACTED] or review.

17.252 For all memberships, including MCJ and MCA, ship all specimens and accompanying materials to the ACCRU Research Base:

[REDACTED]

17.253 The ACCRU Operations Office will forward the diagnostic slides to Dr. [REDACTED] for central review to confirm diagnosis of MCL.

17.3 Paraffin Embedded Tissue Blocks/Slides (Mandatory research tissue)

17.31 Submit one formalin fixed paraffin-embedded (FFPE) tumor tissue block from the most recent tumor tissue biopsy. **A corresponding H&E slide from the submitted block must be provided** to permit quality assessment (QA) of the tissue block. Once the QA is completed, the H&E slide will be returned, unless specified otherwise in section 17.29.

17.32 The FFPE tissue block is preferred; however, **if an institution is unable to provide a tissue block**, cut (15) 4-micron sections and mount sections on charged glass slides. **Label the slides with ACCRU patient ID number, accession number, and order of sections (i.e., 1-11). (1) four micron slide for the H&E stain the first cut slide (i.e., slide labeled 1).** This slide will be reviewed centrally under the research base's protocol for assessing tissue quality. **Do not bake or place covers slips on the slides.**

17.33 The following materials below are required (unless indicated otherwise) for shipment:

- Paraffin Embedded Tissue Blocks with Corresponding H&E Slide (or 15 Unstained Slides with Corresponding H&E Slide)
- Research Tissue Submission Form
- Surgical Pathology Report
- Operative Report (*optional*)

Note: Please include the ACCRU patient ID number on all materials listed above.

17.34 The block/slides/cores must be appropriately packed to prevent damage (e.g., slides should be placed in appropriate slide container) and placed in an individual plastic bag. Label the bag with the protocol number, ACCRU patient ID number, and patient initials.

17.35 Tissue specimens must be shipped ≤ 30 days after registration.

17.36 Verify that the appropriate sections of the Tissue Specimen Submission Form are completed and filled in correctly. Enter information from the Tissue Specimen Submission Form into the remote data entry system on the same day the specimen is submitted (see Forms Packet).

- 17.37 Ship all block/slide tissue specimens and accompanying materials to the ACCRU Research Base:

- 17.38 If corresponding H&E slide was not submitted with the tissue specimen, the ACCRU Operations Office will request a slide to be processed (i.e., cut and H&E stained) from the tumor tissue block. Processing will be performed in the Pathology Research Core (PRC), Mayo Clinic Rochester.

- 17.39a The ACCRU Operations Office will forward the blocks and/or H&E slide(s) to [REDACTED] and colleagues to be reviewed under the research base's protocol for assessing tissue quality for the proposed correlative studies.

- 17.39b After the pathologist assesses the tissue quality, the block and appropriate paperwork will be returned to the ACCRU Operations Office.

